A prospective randomized clinical trial evaluating the effect of convective pre-warming on intra-operative thermoregulatory capabilities in patients enrolled in the TIGER anesthesia perioperative protocol

PI: [name], BS¹
Medical Student

Co-PI: [name], MD²
Professor

Co-I: [name], CRNA²

Co-I: [name], RN²

Co-I: [name], MPH²

¹University of Missouri School of Medicine

²Department of Anesthesiology and Perioperative Medicine

University of Missouri
[name]

NCT03876808

Contact: [name], BS

University of Missouri School of Medicine

[name]

[name]

[contact]

Email: [contact]

Summary

This prospective randomized clinical trial will assess the effect of pre-operative convective warming on intra-operative thermoregulation in patients undergoing gastrointestinal or genitourinary surgical procedures with the TIGER* anesthesia perioperative protocol.

*See addendum 1

Objectives:

Primary Endpoint:

1. Change in core temperature between induction of anesthesia and end of skin preparation (but before turning on the operating room forced-air warmer) as measured by a temperature-sensing Foley catheter

Secondary Endpoints:

1. Change in skin temperature between arrival to the holding area and departure to the operating room
2. Intraoperative temperatures
3. Skin temperature on arrival to the PACU (post-anesthesia care unit)
4. Differences in temperature changes between elderly (≥ 65 years) and younger patients

Clinical Hypotheses:

Primary Hypothesis:

We hypothesize that patients who are convectively warmed at 43°C for at least 60 minutes pre-operatively will have a higher core body temperature during the intraoperative period as measured by a temperature-sensing Foley catheter

Exploratory Hypothesis:

Patients who are convectively warmed prior to surgery will have

1. Temperatures that are significantly increased
 - a. At departure from the preoperative holding area

- b. In the OR after surgical preparation
 - c. On arrival to the PACU
2. Older (age \geq 65 years) patients will demonstrate a greater change in mean intraoperative temperature compared to younger patients

Background & Rationale:

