was a significant difference in severity of hypothermia when it did occur.¹³ This study focused only on men undergoing transurethral resection of the prostate however, and suffers from lack of generalizability. With the proportion of the geriatric population continuing to expand, and the potential adverse effects resulting from their increased susceptibility to intraoperative hypothermia, it is of the utmost importance to look into methods to counter this dilemma and expand the database on the topic.

Study Design:

This will be a prospective randomized clinical trial performed at a single academic hospital. Due to the nature of the trial, the anesthesiologists and subjects will not be blinded to their group assignment, but the postoperative assessments will be. All subjects will receive standardized pre-operative preparations, induction, and intraoperative infusions, as dictated by the TIGER anesthesia perioperative protocol.

In addition to these measures, one group will undergo convective warming during the preoperative preparations, completed for a minimum of 60 minutes prior to entering the operating room, while the other group will undergo standard of care, which includes providing each patient with a warming gown that is not turned on as well as blankets and sheets with more blankets provided on patient request.

Study Procedures:

- I. Patient population: 40 patients undergoing gastrointestinal or genitourinary surgeries, who are enrolled in the TIGER anesthesia perioperative protocol
- II. Inclusion criteria:
 - a. ASA I-IV
 - b. Other inclusion criteria as delineated in the TIGER anesthesia perioperative protocol
- III. Exclusion criteria:
 - a. Inability to obtain written informed consent
 - b. Inability to obtain Foley catheter temperature recordings
 - c. Family history of malignant hyperthermia
 - d. Preoperative temperature $> 38^{\circ} \text{ C}$
 - e. Other exclusion criteria as delineated in the TIGER anesthesia perioperative protocol
- IV. Randomization: On the day of surgery, patients will be randomized to one of two groups:
 1. Warming group: This group will undergo pre-warming at a temperature of 43° C or a minimum of 60 minutes beginning upon arrival to the pre-operative room continuing until they are taken to the operating room. This will be achieved with blankets as well as the use of a Bair Hugger® heating gown.

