 2. Standard of care group: this group will receive the standard of care during the preoperative period, which includes providing the patient with blankets and sheets, as well as additional blankets upon request. They will also wear a Bair Hugger® heating gown, but it will not be used for preheating prior to surgery.

V. Randomization will be stratified for the type of surgery (gastrointestinal versus genitourinary) in an effort to reduce confounding.

VI. Blinding: Due to the nature of this study, the anesthesiologist, nursing staff, operating room staff, and the subject will know to which group the subject has been assigned.

VII. Anesthetic management as outlined in the enhanced recovery protocol.

VIII. Postoperative pain management as outlined in the enhanced recovery protocol.

IX. Perioperative assessments

- a. Duration of pre-warming prior to surgery
- b. Temperature change from arrival in the pre-operative holding area to leaving for the operating room as measured by a skin-temperature thermometer.
- c. Temperature change, as measured by a Foley catheter sensor inserted, after induction of anesthesia to the end of surgical skin preparation.
- d. Temperature as measured with a Foley catheter sensor throughout the operative procedure.
- e. Temperature change between leaving the operating room and arrival in the Post Anesthesia Care Unit (PACU).
- f. Duration of hospital stay, estimated blood loss, transfusion requirements, and postoperative complications

X. Sample size and statistical consideration:

- a. This is a pilot study and, if pre-warming is successful at preventing intraoperative hypothermia, data from this study will be used to develop larger studies. We plan to enroll 20 patients per group for a total sample size of 40 subjects to obtain pilot data.
- b. Data will be analyzed using chi-square and t-tests as appropriate with $p < 0.05$ considered significant.

Risks:

- I. No adverse effects are currently expected through participation in this study other than possible sweating and discomfort in patients in the pre-warming group heated for more than one hour.
 - a. Patients in the pre-warming group will be warned of the potential for sweating or discomfort due to warmth during informed consent at the pre-operative clinic visit. If they feel uncomfortable during the pre-warming process, staff will turn down the warmers from 43C to 38C; if symptoms persist staff will turn the warmers off.

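### The PACU temperature is defined as an arrival level in the endpoint and hypothesis but listed as a change from operating-room exit, which removes any warming effect already present at exit

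*Combined protocol and SAP*

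**What the plan says.** **The outcome as a level.** In Objectives, secondary endpoint 3 is "Skin temperature on arrival to the PACU (post-anesthesia care unit"). Exploratory hypothesis 1 predicts "Temperatures that are significantly increased" in pre-warmed patients, and item 1c places this "on arrival to the PACU". Hypothesis 1c names no sensor; endpoint 3 names skin.

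**The outcome as a change.** In Study Procedures, section IX, the one item covering PACU temperature is IX.e: "Temperature change between leaving the operating room and arrival in the Post Anesthesia Care Unit (PACU"). It names no sensor. The neighbouring items do: IX.b is "Temperature change from arrival in the pre-operative holding area to leaving for the operating room as measured by a skin-temperature thermometer", and IX.d is "Temperature as measured with a Foley catheter sensor throughout the operative procedure". No skin reading at operating-room exit is listed anywhere.

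**Timing of the intervention.** Under IV, warming runs "beginning upon arrival to the pre-operative room continuing until they are taken to the operating room". It is over before the exit reading is taken. The primary hypothesis is that warmed patients "will have a higher core body temperature during the intraoperative period as measured by a temperature-sensing Foley catheter", so the plan itself expects treatment to shift temperatures during surgery.

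**Analysis.** Section X.b provides for chi-square and t-tests at the 0.05 level. It does not say whether the PACU level or the operating-room-to-PACU change is compared.

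**The concern.** The plan defines the PACU outcome in two ways that answer different questions. The level asks whether warmed patients are warmer when they reach the PACU. The change asks whether they gain or lose heat differently during the transfer, having first subtracted whatever benefit they brought out of the operating room.

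If the change were taken as the PACU result, a real benefit could appear as no difference or as harm. Because X.b leaves the choice open, it could also be made after the data are seen. Section X.a says the data are meant to inform larger studies, so a PACU estimate that is attenuated or has the wrong sign could mislead their planning.

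**Working it through.** **Inputs from the documents.** 20 patients per group, 2 × 20 = 40 in total, and p < 0.05 (X.a, X.b). The plan gives no effect size, SD or power, so there is no further design figure to reproduce.

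**Assumptions, not in the documents.** Two-sided testing; SD 0.5 °C at each time; correlation ρ between exit and PACU readings of 0.3 to 0.8; one temperature scale at both times; effects as shown below.

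**Step 1, algebra.** Let D_O be the between-arm effect at operating-room exit and D_P the effect at PACU arrival.

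- Difference in level at PACU = D_P
- Difference in change = D_P - D_O

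The two agree only when D_O = 0. If D_O = D_P, the change shows nothing. If D_O exceeds D_P, the change is negative even when D_P is positive. This does not depend on the SD or the correlation.

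**Step 2, a simple illustration.** Take D_O = 0.4 °C, of which a fraction c carries to the PACU. The level effect is 0.4c and the change effect is 0.4c - 0.4.

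- c = 1: level +0.4 °C, change 0
- c = 0.75: level +0.3 °C, change -0.1 °C
- c = 0.5: level +0.2 °C, change -0.2 °C

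**Step 3, effect on the test.** SD of the change = 0.5 × √(2(1 - ρ)), which is 0.592, 0.500 and 0.316 °C at ρ = 0.3, 0.5 and 0.8. Power is from the noncentral t with 38 degrees of freedom and noncentrality (difference/SD) × √(20/2). For a 0.5 °C level effect this is 1.0 × √10 = 3.16, giving power 0.87.

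| D_O | D_P | Level: power | Change: expected difference | Change: rejection rate at ρ = 0.3 / 0.5 / 0.8 |
|---|---|---|---|---|
| 0.5 | 0.5 | 0.87 | 0 | 0.05 / 0.05 / 0.05 |
| 0.5 | 0.4 | 0.69 | -0.1 | 0.08 / 0.10 / 0.16 |
| 0.5 | 0.25 | 0.34 | -0.25 | 0.26 / 0.34 / 0.68 |
| 0.3 | 0.5 | 0.87 | +0.2 | 0.18 / 0.23 / 0.50 |
| 0 | 0.5 | 0.87 | +0.5 | 0.74 / 0.87 / 1.00 |

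In rows two and three the expected change has the wrong sign. In the last row, with no effect at exit, the change estimates the right quantity, and at ρ = 0.8 it is the more powerful test.

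**Step 4, value of the pre-warming baseline.** If r is the within-arm correlation between holding-area arrival and PACU-arrival skin temperature, adjustment multiplies the residual variance by 1 - r². The reduction is 1% at r = 0.1, 9% at r = 0.3 and 36% at r = 0.6. The documents give no value of r. Adding the baseline and the surgery stratum lowers the residual degrees of freedom from 38 to 36.

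**The case against.** Several points on the other side have force.

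**The sensor.** A reader might infer that IX.e must be a skin value minus a bladder value, because endpoint 3 is on skin and the Foley catheter is the only sensor named during surgery. The text does not establish this. IX.e names no sensor, and skin at both ends or Foley at both ends remains open. What stands is that the sensor is unspecified and could differ between the two times.

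**Size of any sensor offset.** A reader might take the 4 °C periphery-to-core gradient in Background & Rationale as the size of the resulting error. There it defines a vasoconstriction threshold; it is not an expected difference between sensors at these times. An offset common to both arms would also cancel in the comparison. Only an offset that differed by arm would bias it, and the documents give no figure for that.

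**Whether the hypothesis can be tested.** A reader might conclude that the trial cannot test hypothesis 1c. That goes too far. Computing the change requires a PACU-arrival reading, and endpoint 3 itself calls for the level. If that reading is taken on skin and kept as a raw value, the test is available. X.b never says the change is the test of 1c. But IX.e guarantees neither the sensor nor the raw value.

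**The role of section IX.** It is not purely a list of endpoints: IX.a and IX.f match no listed endpoint. The change could stand as a description of the transfer period, so removing it altogether is a matter of preference.

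**Size of the exit effect.** It may be small. The plan refers to an operating-room forced-air warmer switched on after skin preparation, and the background cites benefits lasting 75 to 90 minutes, or up to 2 hours, after induction. A smaller exit effect means a smaller distortion. The same time limits, however, make a fading effect plausible, and that is the pattern that reverses the sign.

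**Adjustment.** An unadjusted t-test of the level is valid under randomisation. Adjustment is a gain in precision of unknown size, and at r = 0.1 it is negligible.

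**Conclusion.** The inconsistency is real and follows from the text alone: the endpoint and hypothesis are an arrival level, the listed assessment is a change from a post-treatment value, and the analysis section does not choose between them. The algebra rests on no assumed figure.

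The size of the distortion equals the effect at operating-room exit, which the documents do not give. Under the assumed inputs it ranges from none (no exit effect) to a full sign reversal (+0.25 °C on the level, -0.25 °C on the change). When equal effects of 0.5 °C are present at both times, power is 0.87 for the level and 0.05 for the change.

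The point affects one secondary endpoint and one exploratory hypothesis in a 40-patient pilot. The primary endpoint is untouched. The correction is worth making because it costs almost nothing and the data are intended for planning later studies.

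**What to change.** 1. Reword IX.e so that skin temperature on PACU arrival is recorded as its own value, with the same thermometer and body site as IX.b.
2. In X.b, state that secondary endpoint 3 and hypothesis 1c are assessed by comparing arms on that level, in a linear model with arm, holding-area arrival skin temperature and surgery type (gastrointestinal or genitourinary, the randomisation stratum). State that the arrival reading is taken before the gown is switched on, and keep it as a raw value as well as within the IX.b change.
3. If an operating-room-to-PACU change is still wanted, label it descriptive and name one sensor for both ends.

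Items 1 and 2 cost one line in section IX and one in X.b. They use a thermometer and a baseline reading already in the plan, add no patient burden, and use two degrees of freedom in the analysis. Item 3 is optional; on the skin scale it would need a reading at operating-room exit that is not now listed.

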By the year 2030 the geriatric presence in the United States, defined as any adult >65 years of age, is estimated to reach around 20% of the entire population.¹ Thus, understanding medical concepts as they relate to the elderly is becoming increasingly important. One such concept is that of hypothermia - a core body temperature $< 36^{\circ}\text{C}$ - for which age >65 has been found to be an independent risk factor.² This complication is especially prevalent intra-operatively due to use of general anesthetics, cool ambient operating room (OR) temperatures, and impaired thermal regulation in the elderly.³

The human body employs numerous mechanisms to maintain thermal homeostasis including: behavioral means of thermoregulation, sweating, pre-capillary vasodilation, non-shivering and shivering means of heat production, and arteriovenous shunt vasoconstriction.⁴ The first, and arguably most important, regulatory response to occur is that of vasoconstriction, which normally results in redistribution of blood from the relatively cool periphery to the warmer core compartment in order to confine metabolic heat to the central tissues.^{2,5} Patients undergoing general anesthesia experience reduced vasoconstriction due to decreased cold response thresholds while patients undergoing epidural anesthesia experience sympathetic blocks resulting in blunted vasoconstrictive responses.^{2,5} All patients experience the afore mentioned side effects of anesthetics, however it has been proven that the elderly are more susceptible to hypothermia due to lower vasoconstriction thresholds - determined by a temperature gradient of 4°C between the periphery and core.

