First explored by *Kurz et al.*⁶ in 1993, it was found that use of nitrous oxide and isoflurane anesthesia lead to an approximately 1.2°C lower vasoconstriction threshold of 33.9 ± 0.6 in the elderly versus 35.1 ± 0.3 in the young ($p < .01$). This subject was again looked at in a 1997 study wherein the vasoconstriction threshold during nitrous oxide and sevoflurane was observed to be decreased by approximately 0.8°C in the elderly at 35.0 ± 0.8 versus 35.8 ± 0.3 in the young ($p < .01$).⁷ This is relevant because intraoperative hypothermia has long been known to lead to adverse outcomes such as increased incidence of myocardial ischemia, arrhythmias, coagulopathic states, and wound infections.⁴ In a 2014 retrospective cohort study by *Billeter et al.*² patients experiencing core temperatures $<35^\circ\text{C}$ had a four times increase in mortality with complication rates increasing two fold and incidence of stroke increasing six fold. To counter this thermoregulatory failure in patients, numerous methods of warming have been practiced over time to augment the normal body response.

One method used to decrease intraoperative hypothermia is warming patients before surgery via skin surface warmers. Numerous studies have found that even brief periods of pre-warming can improve intraoperative temperatures significantly for as long as 75-90 minutes after induction.^{8,9} In procedures lasting less than 90 minutes, *Horn et al.*¹⁰ found that as little as 10 minutes of pre-warming decreased incidence of intraoperative hypothermia from 69% to just 13% while *Torossian et al.*¹¹ decreased the incidence from 60% to 38% in his study using a self-warming blanket for 30 minutes pre-operatively. Studies have also shown that longer pre-warming of 45-60 minutes can prevent hypothermia for up to 2 hours after induction.¹²

[figure not shown]
While significant research has been performed on the effects of warming patients before they undergo surgical procedures, scant evidence demonstrates the effect of pre-warming in the elderly. In one article specifically looking at pre-warming in the elderly (mean age ~72-73) it was found that, after pre-warming for 20 minutes, there was no significant change in incidence of hypothermia but there

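### The outcome that section X.a ties larger studies to, intraoperative hypothermia, is not a planned endpoint, and X.b's t-tests leave out the surgery-type factor used to stratify randomization

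*Combined protocol and SAP*

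**What the plan says.** Study Procedures X.a calls the trial a pilot of 20 patients per group and says that "if pre-warming is successful at preventing intraoperative hypothermia, data from this study will be used to develop larger studies".

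The endpoints, listed under Objectives, are all temperatures or temperature changes. The primary is "Change in core temperature between induction of anesthesia and end of skin preparation (but before turning on the operating room forced-air warmer" is turned on. Secondary endpoint 2 reads in full "Intraoperative temperatures". The other three are a preoperative skin temperature change, skin temperature on arrival in the PACU, and age differences in temperature change. The primary hypothesis is a "higher core body temperature during the intraoperative period". A mean is mentioned only in the exploratory age hypothesis: "greater change in mean intraoperative temperature compared to younger patients".

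Assessments IX.a to IX.f cover duration of warming, temperatures (IX.d is the Foley temperature through the whole operation), hospital stay, blood loss, transfusion and complications. Hypothermia is defined once, in Background & Rationale: "One such concept is that of hypothermia - a core body temperature" below 36 °C.

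Section V stratifies randomization by gastrointestinal versus genitourinary surgery. Section X.b names only chi-square tests and t-tests, used where appropriate, with significance at p < 0.05.

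**The concern.** X.a names one outcome as the reason to go on to larger studies, and the endpoints measure another. A smaller temperature drop up to the end of skin preparation does not show that fewer patients fell below 36 °C during the operation. The Background itself cites a study in elderly men in which pre-warming changed the severity of hypothermia but not its incidence, so the two can part company.

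If incidence is worked out afterwards, someone must choose how many readings count as an event and over what period. Nothing in the plan prevents that choice from being made after temperatures by arm are known. The next study's sample size would then rest on it.

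A second and separate point concerns X.b. Stratified randomization balances surgery type across arms, but a two-sample t-test leaves the variation due to surgery type in its error term. If surgery type affects temperature, the standard error is too large and a trial of 40 loses some of its power.

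**Working it through.** **The plan's own figure.** 20 + 20 = 40, which agrees. X.a gives no power, effect size, SD or event rate, so there is no sample-size calculation to reproduce.

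**Hypothermia against the listed outcomes.** This part needs no arithmetic.
- Primary endpoint: a continuous change that ends at skin preparation. Its start also needs care. Objectives starts it at induction, while Ethical Considerations II.b places the catheter after induction, so the first Foley reading comes later than induction.
- Secondary endpoints 1 to 4: temperatures or changes, none classified against 36 °C.
- IX.a to IX.f: no hypothermia item. IX.d does supply the readings from which one could be built.
- Missing: a rule for counting an event, a period, and a place for the result among the endpoints.

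**What 20 per arm can say about incidence.** The only incidences in the documents are two pairs cited in the Background: one study "decreased incidence of intraoperative hypothermia from 69% to just 13" percent, and another "decreased the incidence from 60% to 38% in his study using a self-warming blanket for 30 minutes pre-operatively". They come from other settings and serve only as illustration.

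Newcombe interval for a risk difference d = p1 − p2, with Wilson limits (l, u) in each arm: lower limit d − √[(p1 − l1)² + (u2 − p2)²], upper limit d + √[(u1 − p1)² + (p2 − l2)²]. Averaged exactly over both binomials with n = 20 per arm:

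| True incidence | Mean half-width | Newcombe coverage | Wald coverage | Exact chi-square power |
|---|---|---|---|---|
| 60% vs 38% | 27 points | 94.9% | 92.5% | 26% |
| 69% vs 13% | 24 points | 95.0% | 93.3% | 97% |

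For a later study with 80% power at two-sided 0.05, n per arm = [1.96√(2p̄q̄) + 0.842√(p1q1 + p2q2)]² / d², where p̄ is the average of the two rates.
- 60% vs 38%: (1.386 + 0.580)² / 0.0484 = 79.9, so 80 per arm.
- 69% vs 13%: (1.363 + 0.481)² / 0.3136 = 10.9, so 11 per arm.

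Incidence by arm is therefore a main planning input for the next study.

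**t-test against a model adjusted for surgery type.** Assumptions, none from the documents: arm effect 0.9 SD, normal errors, 10 patients per surgery type per arm, and a surgery-type effect of s SD. Balance means that the true variance of the arm difference is unaffected by s. The t-test's pooled variance is inflated by about 1 + (s²/4)(20/19):
- s = 0.5: 1 + 0.0625 × 1.0526 = 1.066, so the standard error is about 1.03 times too large.
- s = 1: 1 + 0.25 × 1.0526 = 1.263, about 1.12 times too large.

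Approximate power of the t-test is Φ(0.9√10 − 2.024 × inflation): Φ(2.846 − 2.090) = 77.5% at s = 0.5, and Φ(2.846 − 2.275) = 71.6% at s = 1. Simulation of 40,000 trials per setting gives:

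| Surgery-type effect | Type I error, t-test | Type I error, adjusted | Power, t-test | Power, adjusted |
|---|---|---|---|---|
| 0 SD | 4.9% | 5.0% | 78.9% | 78.8% |
| 0.5 SD | 4.2% | 5.0% | 77.5% | 79.3% |
| 1 SD | 2.9% | 5.0% | 72.0% | 79.6% |

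The power losses are −0.1, 1.8 and 7.6 points, that is about 0, 2 and 8. With permuted blocks of 4 in place of exact balance, the 1 SD row becomes 3.0% and 72.4% for the t-test against 5.1% and 79.8% adjusted.

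**The case against.** X.a is one loosely worded sentence in a pilot protocol. It sets no threshold, test or gate, and a reader who infers a formal go/no-go rule would be reading in something that is not there. The stated hypothesis is higher core temperature, and the endpoints do measure that. This stands, and it limits the weight of the point.

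Nor do the documents support saying that hypothermia incidence cannot be produced. The Background gives a threshold, IX.d gives the readings, and chi-square tests in X.b imply that some categorical outcome is expected. What is missing is the rule and the commitment to report it. The recording interval may be set in the TIGER addendum or the enhanced recovery protocol, to which this protocol defers and which could not be checked.

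The lack of a per-patient summary for secondary endpoint 2 is, taken alone, mostly missing detail.

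On X.b, the unadjusted t-test is valid. Its error rate is below 5%, and no figure in the documents shows that surgery type shifts temperature by as much as 1 SD. What remains is that adjustment costs almost nothing when surgery type has no effect and helps when it has one.

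**Conclusion.** The point holds in a limited form. The outcome that X.a names is not a planned result, and its definition is left open to choice after the data are seen. This rests on the text alone, subject to the unavailable addendum. The plain t-tests are conservative, at a cost of about 0 to 8 power points over the assumed surgery-type effects of 0 to 1 SD, with type I error near 3% at the top of that range. The effect sizes are assumptions.

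Two stronger inferences should be resisted. The 26% and 97% power figures do not show that 40 patients is the wrong number: the trial is a pilot and the rates come from other settings. And no size can be put on how far the choice of counting rule, window or recording interval would move the incidence here. The documents give no intraoperative temperature profile, and a model with constant mean temperatures would ignore the operating-room warmer and the fading benefit that the Background describes.

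This is a change worth considering. It does not undermine the trial.

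**What to change.** 1. Add a secondary endpoint: the proportion of patients with Foley core temperature below 36 °C on two consecutive readings, from the first reading after catheter insertion to the end of surgery, at the routine recording interval. A shorter window is acceptable if it is fixed before any look at data by arm. Report the risk difference with its Newcombe 95% CI.
2. Reword X.a to say that this estimate and its interval will inform the design of a larger study, and that no significance test on it decides whether that study is developed.
3. In X.b, replace the t-test for the primary and the other continuous temperature endpoints with a linear model of arm adjusted for surgery type. For secondary endpoint 2, use one time-weighted mean per patient.

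The cost is a few lines of wording. The readings are already planned and no patients are added. The interval will be wide, about ±24 to 27 points at the cited incidences, and should be presented as such. Adjustment uses one degree of freedom (38 to 37), with no visible loss of power when surgery type has no effect (78.8% against 78.9%).

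### Randomisation is stratified by surgery type but the analysis is a plain t-test; adding the stratum term is a near-free gain in precision if surgery type predicts temperature change

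*Combined protocol and SAP*

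**What the plan says.** All references are to the combined protocol and SAP.

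- **Study Procedures V:** "Randomization will be stratified for the type of surgery (gastrointestinal versus genitourinary) in an effort to reduce confounding".
- **Study Procedures X.b:** "Data will be analyzed using chi-square and t-tests as appropriate", with p < 0.05 "considered significant". This is the entire analysis plan. Nothing in the document names a model, a covariate, a stratified test or any analytic use of surgery type.
- **Objectives, Primary Endpoint:** the primary outcome is continuous, "Change in core temperature between induction of anesthesia and end of skin preparation", so the t-test is in effect the primary analysis.
- **Study Procedures IX.b:** the first secondary endpoint is a raw skin change, "Temperature change from arrival in the pre-operative holding area to leaving for the operating room as measured by a skin-temperature thermometer".
- **Study Procedures IV.1:** warming is given "beginning upon arrival to the pre-operative room continuing until they are taken to the operating room". The plan does not say whether the arrival skin reading comes before the warmer is switched on.
- **Study Procedures X.a:** "We plan to enroll 20 patients per group for a total sample size of 40 subjects to obtain pilot data". The same item adds: "This is a pilot study and, if pre-warming is successful at preventing intraoperative hypothermia, data from this study will be used to develop larger studies".

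**The concern.** Choosing surgery type as the stratification factor implies that the sponsor thinks it may relate to outcome. If it does, and the arms are balanced within each stratum, the true sampling variability of the arm difference is already reduced by the design. A plain t-test does not credit this. It leaves the between-stratum variance in its error term, reports too large a standard error, and runs below its nominal type I error. The estimate stays unbiased and the error is conservative, so there is no false-positive risk.

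What is lost is precision. With 40 patients whose data are meant to inform larger studies, the width of the interval is one of the trial's main products.

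A second, smaller point is of the same kind. The arrival skin temperature is already recorded but is only subtracted from the departure value. Using it as a covariate is at least as precise, provided it is a true pre-warming reading.

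**Working it through.** **Inputs from the document.** 20 per arm, 40 in total (X.a); significance level 0.05 (X.b; two-sided assumed); two strata (V). There is no power calculation to reproduce.

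**Assumptions.** True effect 0.8 SD. Surgery type explains R² = 0, 5, 10, 20 or 30% of the within-arm variance. Strata of 20/20, with 32/8 as a check. The document mentions no blocking, so allocation is taken first as balanced within strata, then as 20:20 overall without that balance.

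**1. Cost of the extra term.** Error degrees of freedom fall from 38 to 37 and the critical t value rises from 2.0244 to 2.0262, a ratio of 1.0009. With balance and R² = 0, the interval is 0.1% wider and power is 69.3% either way.

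**2. Gain with balance within strata (20/20 strata, 10:10 in each).**

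- Adjusted power comes from the noncentral t with 37 df and noncentrality 0.8 × √10 / √(1 − R²), where √10 = 1/√(1/20 + 1/20). At R² = 0, 10, 20 and 30% the noncentrality is 2.530, 2.667, 2.828 and 3.024.
- The expected t-test error variance is [38(1 − R²) + 40R²]/38 = 1 + 2R²/38. The adjusted error variance is 1 − R². The ratio of interval widths, t-test to adjusted, is about √[(1 + 2R²/38)/(1 − R²)] × 2.0244/2.0262.
- Type I error and t-test power come from simulation, 20,000 trials per cell.

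| R² | t-test type I error | t-test power | Adjusted power, simulated (exact) | Width ratio, t-test / adjusted |
|---|---|---|---|---|
| 0% | 5.2% | 69.6% | 69.5% (69.3%) | 0.999 |
| 5% | 4.4% | 69.7% | 71.5% (71.5%) | 1.026 |
| 10% | 3.8% | 70.2% | 73.9% (73.8%) | 1.056 |
| 20% | 2.8% | 71.1% | 79.0% (78.7%) | 1.123 |
| 30% | 2.1% | 71.4% | 83.6% (83.8%) | 1.204 |

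Strata of 32/8 at the same R² give nearly the same adjusted power: 69.5, 71.5, 73.9, 78.2 and 83.9%. A larger assumed effect of 0.909 SD, which gives the t-test 80% power at R² = 0, shows the same pattern. At R² = 10, 20 and 30%, power goes from about 81, 82 and 84% to 84, 88 and 92%.

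**3. Without balance within strata (20/20).** The t-test holds its level at about 5%. At R² = 0, 5, 10, 20 and 30%, power is 69.1, 69.2, 69.2, 68.9 and 68.6% for the t-test and 67.7, 70.2, 72.4, 77.3 and 82.5% adjusted. The loss at R² = 0 is 69.1 − 67.7 = 1.4 points; repeat simulations put it between 1.3 and 1.6. Break-even is where the gain offsets chance imbalance. The expected squared correlation between arm and stratum is 1/39 = 2.6%, so break-even lies near R² = 2.6%. Simulation agrees: 69.5% versus 69.0% at R² = 2%, and 68.9% versus 70.0% at 5%.

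**4. What these R² values require.** With equal strata the gap between surgery types is √(R²/0.25) total SDs: 0.63, 0.89 and 1.10 SD for R² = 10, 20 and 30%. With 32/8 strata the same gaps explain less. For 0.63 SD: 0.40 × 0.8 × 0.2 = 0.064, and 0.064/(0.064 + 0.90) = 6.6%. The other two give 13.8% and 21.5%.

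**5. Skin endpoint.** Let k be departure SD over arrival SD, the same in both arms, and ρ their correlation. The variance of the arrival-adjusted analysis relative to raw change is k²(1 − ρ²)/(1 + k² − 2ρk).

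- k = 1: (1 + ρ)/2 = 0.65, 0.75, 0.85 at ρ = 0.3, 0.5, 0.7.
- k = 1.5: 2.0475/2.35 = 0.87, 1.6875/1.75 = 0.96, 1.1475/1.15 = 1.00.

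**The case against.** The strongest reply is that nothing in the document shows surgery type to be prognostic for this endpoint. The primary window closes at the end of skin preparation, before the operation begins, and induction and infusions are standardised. The background section supports age as a predictor, not surgery type. A 1.10 SD gap between surgery types over that interval would be large, so the 30% row should not drive the judgement. Below about 2.6% of variance explained, and without balance within strata, adjustment loses slightly. The t-test is valid, the trial is a pilot with no power claim, and stratification has already served its stated purpose in the design.

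All of that stands, and it limits the expected benefit. It does not reverse the recommendation: the largest loss found is about 1.3 to 1.6 points of power, against a gain of about 4 to 8 points at 10 to 20% of variance.

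A second objection is that a general rule for continuous outcomes does not deal with repeated intraoperative temperatures, the comparison of older and younger patients, or the shape of hospital stay and blood loss. That is true, but the t-test in X.b does not deal with them either. A model with arm and stratum contains the t-test as a special case, so no outcome is handled materially worse than now.

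For the skin endpoint, the gain depends on the SDs and the correlation, and it vanishes in one of the cases shown.

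**Conclusion.** The point holds as a free improvement. Randomisation uses surgery type and the analysis does not. With an assumed 0.8 SD effect, equal strata and balance within strata, the t-test interval is about 3, 6 or 12% wider than needed if surgery type explains 5, 10 or 20% of the variance. Power forgone is about 2, 4 or 8 points. If surgery type explains nothing, the cost is effectively zero with balance and about 1.4 points without it.

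The size is uncertain because the documents give no SD, effect size, stratum effect or stratum sizes. The planned test is not invalid. For the skin endpoint, adjusting for the arrival value cuts variance by 15 to 35% if the SDs are equal at both times, and by 0 to 13% if the departure SD is 1.5 times the arrival SD.

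**What to change.** In X.b, write: *Continuous outcomes, including the primary change in core temperature, will be compared with a linear model containing arm and surgery type; the adjusted mean difference with its 95% confidence interval will be reported. Departure skin temperature will be modelled on arm, surgery type and arrival skin temperature.*

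In IX.b, add that the arrival skin reading is taken before the warmer is switched on. Without that, the reading may already carry part of the warming effect and is not a clean baseline, either for a change score or as a covariate.

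Arrival skin temperature could also be added to the core-temperature model. Its correlation with a change measured after induction is unknown, so no gain is claimed for that.

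The cost is two sentences in X.b and one timing line in IX.b. No new variable is collected, since surgery type must be known in order to randomise. The core endpoint loses one degree of freedom and the skin endpoint two. The text should be fixed before data are analysed, so that adjustment cannot appear to have been chosen after seeing the results.
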